11. ADVERSE EVENTS

11.1. Information on Reporting Adverse Events

11.1.1. Definitions

- *Adverse event (AE)*: Any untoward medical occurrence in a patient or clinical investigation subject administered a pharmaceutical product and which does not necessarily have to have a causal relationship with this treatment. An AE can therefore be any unfavorable and unintended sign (including an abnormal laboratory finding, for example), symptom, or disease temporally associated with the use of study treatment, whether or not considered related to the study treatment.
- *Life-threatening adverse event or life-threatening suspected adverse reaction*: An adverse event or suspected adverse reaction is considered "life-threatening" if, in the view of either the investigator or sponsor, its occurrence places the patient or subject at immediate risk of death. It does not include an adverse event or suspected adverse reaction that, had it occurred in a more severe form, might have caused death.
- *Treatment emergent adverse event (TEAE)*: Any event that was not present prior to the initiation of study treatment or any event already present that worsens in either intensity or frequency following exposure to study treatment.
- *Serious adverse event (SAE)*: Any untoward medical occurrence that, at any dose, results in death; is life threatening (i.e., an event in which the patient was at risk of death at the time of the event; it does not refer to an event that hypothetically might have caused death if it were more severe); requires inpatient hospitalization or prolongation of existing hospitalization; results in persistent or significant disability/incapacity; or is a congenital anomaly/birth defect. Important medical events that may not result in death, be life-threatening, or require hospitalization may be considered serious when, based upon appropriate medical judgment, they may jeopardize the patient or subject and may require medical or surgical intervention to prevent one of the outcomes listed in this definition. Examples of such medical events include allergic bronchospasm requiring intensive treatment in an emergency room or at home, blood dyscrasias or convulsions that do not result in inpatient hospitalization, or the development of drug dependency or drug abuse. (See Section 11.2.3 for additional information about SAE reporting.)
- *Suspected adverse reaction*: Any adverse event for which there is a reasonable possibility that the drug caused the adverse event. For the purposes of IND safety reporting, "reasonable possibility" means there is evidence to suggest a causal relationship between the drug and the adverse event. Suspected adverse reaction implies a lesser degree of certainty about causality than adverse reaction, which means any adverse event caused by a drug.
- *Unexpected adverse event or unexpected suspected adverse reaction*: An adverse event or suspected adverse reaction is considered "unexpected" if it is not listed in the investigator brochure or is not listed at the specificity or severity that has been observed; or, if an investigator brochure is not required or available, is not consistent with the risk information described in the general investigational plan or elsewhere in the current

application, as amended. For example, under this definition, hepatic necrosis would be unexpected (by virtue of greater severity) if the investigator brochure referred only to elevated hepatic enzymes or hepatitis. Similarly, cerebral thromboembolism and cerebral vasculitis would be unexpected (by virtue of greater specificity) if the investigator brochure listed only cerebral vascular accidents. "Unexpected," as used in this definition, also refers to adverse events or suspected adverse reactions that are mentioned in the investigator brochure as occurring with a class of drugs or as anticipated from the pharmacological properties of the drug but are not specifically mentioned as occurring with the particular drug under investigation.

11.1.2. Recording of Adverse Events

Adverse events will be reported and recorded in the eCRF from the time of the first dose of study treatment through 30 days after the last dose of study drug or until the start of subsequent antineoplastic therapy, whichever occurs first. That is, if a patient begins a new antineoplastic therapy, the AE reporting period for nonserious AEs ends at the time the new treatment is started.

Adverse events (including laboratory abnormalities that constitute AEs) should be described using a diagnosis whenever possible, rather than individual underlying signs and symptoms. When a clear diagnosis cannot be identified, each sign or symptom should be recorded as a separate AE.

The Investigator should ask the patient non-leading questions to determine if any AEs have occurred during the study, since the last study visit. Adverse events may also be recorded when they are volunteered by the patient, or through physical examination, laboratory tests, or other clinical assessments.

An AE should be followed until its resolution or until it is judged to be permanent, and assessment should be made at each visit (or more frequently, if necessary) of any changes in severity of the event, the suspected relationship to the study treatment, the interventions required to treat the event, and the outcome.

All AEs occurring during the study are to be followed up in accordance with good medical practice until they are resolved, stabilized or judged no longer clinically significant or, if a chronic condition, until fully characterized.

11.1.2.1. Laboratory Test Abnormalities

Laboratory abnormalities that constitute an AE in their own right (i.e., are considered to be clinically significant, induce clinical signs or symptoms, require concomitant therapy, or require changes in study treatment), should be recorded on the AE eCRF. Whenever possible, a diagnosis, rather than a symptom should be provided (e.g., anemia instead of low hemoglobin).

Laboratory abnormalities that meet the criteria for an AE should be followed until they have returned to baseline levels (as measured during the screening visit) or are deemed no longer clinically significant. When an abnormal laboratory or test result corresponds to a sign/symptom of an already reported AE, it is not necessary to separately record the laboratory/test result as an additional event.

A laboratory abnormality that does not meet the definition of an AE should not be reported as an AE. A Grade 3 or 4 event (considered to be severe per NCI CTCAE, v. 5.0) does not automatically indicate an SAE unless it meets the definition of serious as defined in Section 11.1.1 and/or as per

the opinion of the Investigator. A laboratory abnormality that results in a dose being held or modified would, by definition, be an AE and must be recorded as such in the eCRF.

11.1.3. Adverse Event Severity

The term “severe” is used to describe the intensity of an AE; the event itself could be of relatively minor clinical significance (e.g., ‘severe’ headache). This is not the same as a “serious” AE.

The severity of the AE will be graded by the Investigator according to the NCI CTCAE Grading Scale, v. 5.0 (the NCI CTCAE files can be accessed online at the following URL:
<http://evs.nci.nih.gov/ftp1/CTCAE/About.html>

Events that are not specifically defined in CTCAE v 5.0 should be assessed according to the guidance provided on page 2 of the CTCAE v 5.0 document.

11.1.4. Adverse Event Causality

The Investigator will make a judgment regarding the relationship of the AE to study treatment, as defined below.

- Not related: These events will lack a strong temporal relationship of the event to the study treatment, making a causal relationship not reasonably possible. Exposure to other drugs, therapeutic interventions, or underlying conditions may provide a sufficient explanation for the event.
- Related: There is a temporal relationship of the event to the study treatment, and the event is more reasonably explained by exposure to the study treatment than by any other drugs, therapeutic interventions, or underlying conditions.

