11.2.4. Suspected Unexpected Serious Adverse Reactions

Suspected unexpected serious adverse reactions are SAEs that are unexpected and judged by the Investigator or Karyopharm to be related to the study treatment administered. All suspected unexpected serious adverse reactions will be collected and reported to the competent authorities and relevant ethics committees in accordance with the FDA's "Safety Reporting Requirements for Investigational New Drugs and Bioanalytical/Bioequivalence Studies" or as per national regulatory requirements in participating countries.

If required by local regulations, the Investigator is responsible for notifying his/her IRB or local ethics committee of all SAEs.

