12.4.2. Safety Analyses

All safety analyses will be performed on the Safety Population, unless otherwise specified and will be presented by actual treatment arm. Details of the analyses will be described in the SAP.

The safety and tolerability of selinexor will be evaluated by means of drug-related AE reports, physical examinations, and laboratory safety evaluations. The grading of the severity of the AEs will be done according to CTCAE, v.5.0. Investigators will provide their assessment as either the AE is related or not related to study drug.

Treatment-emergent AEs, SAEs, AEs of at least Grade 3 in severity, related AEs, and AEs leading to withdrawal of treatment will be summarized by Arm and in the overall safety population.

Treatment-emergent AEs will be those that start or worsen on or after the first day of study treatment, through 30 days after last dose (or the day before initiation of a new anti-neoplastic treatment, whichever occurs first). Related AEs will be those with an Investigator determination of related to study drug.

Laboratory data will be analyzed by summary statistics over time, as well as by shift tables based on severity.

Continual monitoring of safety data will be performed by the independent Data Safety Monitoring Board (DSMB). Adverse events and concomitant medications will be coded according to medical dictionary for regulatory activities (MedDRA) and WHO Drug, respectively.

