5.1.1.3. Treatment-emergent Treatment-Related Adverse Events (TRAEs)

A TRAE is any TEAE that is assessed by the Investigator as related to study treatment.

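### The two causality levels in Protocol 11.1.4 leave some possibly drug-caused events in neither category, and the Related test is stricter than the protocol's own reasonable-possibility standard

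*Protocol*

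**What the plan says.** Protocol Section 11.1.4 has the investigator judge each AE against two definitions.

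- **Not related:** "These events will lack a strong temporal relationship of the event to the study treatment, making a causal relationship not reasonably possible". A second sentence adds: "Exposure to other drugs, therapeutic interventions, or underlying conditions may provide a sufficient explanation for the event".
- **Related:** the timing fits, and "the event is more reasonably explained by exposure to the study treatment than by any other drugs, therapeutic interventions, or underlying conditions".

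Protocol Section 12.4.2 confirms that there is no third answer: "Investigators will provide their assessment as either the AE is related or not related to study drug".

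Protocol Section 11.1.1 defines a suspected adverse reaction as "Any adverse event for which there is a reasonable possibility that the drug caused the adverse event". For IND safety reporting it takes this to mean that some evidence points to a causal link, and it describes the standard as less certain than that for an adverse reaction.

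The investigator's answer then feeds the analysis and part of the reporting. SAP Section 5.1.1.3 states: "A TRAE is any TEAE that is assessed by the Investigator as related to study treatment". Protocol Section 12.4.2 defines related AEs in the same way. Protocol Section 11.2.4 defines suspected unexpected serious adverse reactions (SUSARs) as "SAEs that are unexpected and judged by the Investigator or Karyopharm to be related to the study treatment administered".

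**The concern.** The two definitions are drawn at different thresholds. Not related turns on whether causation is reasonably possible. Related turns on whether study treatment is the leading explanation. Whatever lies between has no assigned answer, yet the investigator must give one.

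This matters because both arms receive the same regimen and there is no control arm. Investigator attribution is the main way the tables separate drug toxicity from disease, and Protocol Section 12.4.2 names drug-related AE reports among the means of evaluating safety. The call decides every treatment-related row in SAP Sections 5.1.2.1, 5.1.2.2 and 5.2, including related serious events and related deaths. Under SAP Section 5.1.1.1, an event arising after the treatment period is a treatment-emergent AE (TEAE) only if the investigator calls it related, so for those events the call also decides entry to the TEAE tables.

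**Working it through.** The plan gives no figure to reproduce. The check is whether the two definitions cover every event, and whether Related agrees with Section 11.1.1.

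**Step 1. Apply each definition to the same events.**

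| Event | Not related (11.1.4) | Related (11.1.4) | Suspected adverse reaction (11.1.1) |
|---|---|---|---|
| Timing does not fit; causation not reasonably possible | Yes | No | No |
| Timing fits; treatment is the best explanation | No | Yes | Yes |
| Timing fits; causation reasonably possible; another cause equally good | No | No | Yes |
| Timing fits; causation reasonably possible; another cause better | No | No | Yes |

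The last column assumes that there is evidence suggesting causation, as Section 11.1.1 requires. In rows three and four, Not related fails because the timing is present and causation is reasonably possible. Related fails because its test is comparative, so even a tie does not meet it. The two levels are therefore not exhaustive. The same rows show that Related is stricter than Section 11.1.1. The phrase "making a causal relationship not reasonably possible" under Not related is compatible with Section 11.1.1; the conflict lies in the Related definition.

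**Step 2. Look for a rule that closes the gap.**

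- The second sentence under Not related, on other explanations, is permissive and does not remove the condition in the first. Read as a licence to choose Not related, it would send reasonably possible events there, against the sentence before it.
- Protocol Section 12.1.1 and SAP Section 2.2.5 count a missing relationship as related. That covers blank answers, not an answer given under definitions that do not fit.
- No other section says where such an event belongs.

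**Step 3. Ask whether such events arise.** Protocol Section 4.5 reports that attribution in the earlier trial of this combination included a possible level. That level has no clear place on the present scale.

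**Step 4. Scale.** Protocol Section 6.1 plans 20 patients per arm. One patient moved between levels changes an arm's rate by 1/20 = 5 percentage points and the overall rate by 1/40 = 2.5 points, if all are in the safety population. How many would move cannot be derived from the documents.

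**The case against.** The strongest reply is that the documents do not show which box an investigator would tick. Someone who thinks causation reasonably possible cannot properly choose Not related, and might choose Related. This stands against any claim of a systematic undercount of known size. It does not help the plan, because two investigators can then classify the same event differently, and one who follows the Related wording literally will leave it out.

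The next reply is that the analysis impact is bounded. SAP Section 5.1.2 makes TEAEs the main focus. All TEAEs, those of Grade 3 or higher, serious TEAEs and those leading to discontinuation or death are tabulated whatever their causality, and no testing is planned. This also stands: apart from post-treatment events, only the related rows are exposed.

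A reader might infer four stronger things that the documents do not support:

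- **Suspected reactions would escape expedited reporting or review by the Data Safety Monitoring Board (DSMB).** Under Protocol Section 11.2.3 every SAE up to 30 days goes to the sponsor whatever its causality, and a later one is reported if the investigator suspects a causal link, which is not the Related test. Section 11.2.4 lets the sponsor as well as the investigator judge relatedness. Section 13.5.1 has the DSMB review any SAEs.
- **A percentage undercount can be computed by assuming a share of ambiguous events.** Any such share would be invented. Protocol Section 12.4.2.1 counts each patient once per term and allows for the strongest attribution among repeat episodes, so one clearly related episode can keep the patient in the count. The attributed AE rates for 80 mg weekly in Section 4.4 come from a glioblastoma study.
- **The overlapping toxicities in Section 4.5 are the ambiguous events.** That overlap is between selinexor and pembrolizumab, both study treatment, so it creates no doubt between Related and Not related.
- **The missing-as-related rule contradicts Section 11.1.4.** It addresses a different situation.

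**Conclusion.** The wording of Section 11.1.4 is wrong as it stands, in a limited way. Its two levels are not complementary, and Related sits above the threshold that Section 11.1.1 sets. Some events will be classified inconsistently, and treatment-related toxicity will be undercounted wherever Related is applied literally. The effect falls mainly on the related-AE tables, on related serious events and deaths, on post-treatment events that become TEAEs only if related, and on the investigator's part of the SUSAR judgement. SAE reporting is otherwise largely protected.

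The logical finding needs no assumption beyond a literal reading. The extent of misclassification is unknown; the 5-point step per patient assumes that each arm reaches 20 patients in the safety population. The point is worth correcting because the change is small and alters how events enter the results.

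**What to change.** Reword Section 11.1.4 so that the two levels meet at the Section 11.1.1 threshold:

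- **Related:** there is a reasonable possibility that study treatment caused or contributed to the event, even if other causes are also plausible.
- **Not related:** there is no reasonable possibility that it did.

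Use the same wording in the eCRF and SAE form guidance. The SAP definition of a treatment-related AE can stay, since it refers to the investigator's assessment.

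The cost is two sentences, but in a protocol amendment that needs IRB/IEC approval under Section 13.1.1. The reported treatment-related rate may rise. Enrolment status is not visible in the documents; if patients are already enrolled, the SAP or study report should record which definition applied to which events.

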11.2. Serious Adverse Events

See Section 11.1.1 for the definition of an SAE. Please note that SAEs that occur at any time between the signing of the Informed Consent Form up to the first dose of study treatment must be reported (in addition to SAEs that occur after the first dose of study treatment).

11.2.1. Events that Do Not Meet the Definition of a Serious Adverse Event

Elective hospitalizations to administer, or to simplify trial treatment or trial procedures (e.g., an overnight stay to facilitate 24-hour urine collection) are not considered SAEs. A ‘serious’ hospitalization is defined as any inpatient hospital admission that includes a minimum of an overnight stay in a health care facility. An emergency room visit is not considered a hospitalization unless it results in an official admission as an inpatient to the hospital (e.g., undesirable effects of any administered treatment) and must be documented as an SAE.

Progression of the malignancy/disease (including fatal outcomes) should NOT be reported as an SAE during the study or within the safety reporting period. Any sudden or unexplained death must be reported as an SAE. If there is any uncertainty about a finding being due solely to progression of malignancy/disease, the finding should be reported as an AE or SAE, as appropriate.

11.2.2. Recording of Serious Adverse Events

It is the responsibility of the Investigator to record and document all SAEs occurring from the time when the ICF is signed until at least 30 days after the patient has stopped study treatment. All SAEs must be reported on the designated Sponsor's SAE Report Form in addition to being recorded in the eCRF. The original SAE report form must be retained in the Investigator's site file.

All applicable sections of the SAE Report Form must be completed in order to provide a clinically thorough report. The Investigator must assess and record the relationship of each SAE to study treatment and complete the form in English.

See ICH E2A (Clinical Safety Data Management: Definitions and Standards for Expedited Reporting, Attachment 1) for key data elements that are required for expedited reporting.

11.2.3. Reporting of Serious Adverse Events

Every SAE, regardless of the causal relationship to the study treatment, occurring after the patient has signed informed consent, until at least 30 days after the patient has stopped study treatment, must be reported to the Karyopharm Pharmacovigilance. The investigational site personnel must use the SAE Report Form (paper or electronic) provided by Karyopharm for reporting any SAE to the Karyopharm Pharmacovigilance Department. The immediate report should be made by the investigator within a very short period of time and under no circumstances should this exceed 24 hours following knowledge of the SAE. After the 30-day follow-up period SAEs should only be reported to Karyopharm if the Investigator suspects that the SAE has a causal relationship to the study treatment.

To complete the electronic SAE Report Form, a Log Line must first be completed in the AEs eCRF. The SAE will then be linked to an electronic SAE Report Form. It is then necessary to complete a Log Line in the corresponding SAE Report Form eCRF within 24 hours of learning of the SAE's occurrence. It is not necessary to submit a paper SAE Report Form if the SAE was originally declared using the electronic SAE Report Form.

If the SAE is to be reported via a paper SAE Report Form, upon completion, the SAE Report Form must be immediately emailed or faxed to:

Pharmacovigilance Department

Karyopharm Therapeutics Inc.

Email: [contact]

[contact] (USA)

[contact] (Germany)

Recurrent episodes, complications, or progression of the initial SAE must be reported, as follow-up to the original episode, within 24 hours of the Investigator receiving the follow-up information.

An SAE should be followed until its resolution or until it is judged to be permanent. An assessment should be made at each study visit (or more frequently, if necessary) of any changes in severity of the event, the suspected relationship to the study treatment, the interventions required to treat the event, and the outcome of the event.

11.2.4. Suspected Unexpected Serious Adverse Reactions

Suspected unexpected serious adverse reactions are SAEs that are unexpected and judged by the Investigator or Karyopharm to be related to the study treatment administered. All suspected unexpected serious adverse reactions will be collected and reported to the competent authorities and relevant ethics committees in accordance with the FDA's "Safety Reporting Requirements for Investigational New Drugs and Bioanalytical/Bioequivalence Studies" or as per national regulatory requirements in participating countries.

If required by local regulations, the Investigator is responsible for notifying his/her IRB or local ethics committee of all SAEs.

